9.2 Demographics and Subject Disposition

Subject disposition will be listed. The demographic variables age, sex, race, population (Japanese or Caucasian), ethnicity, country of enrolment, site ID, body weight, height and body mass index will be summarized overall and by population, and listed.

Associated person demographic data for individual subjects will be listed.

9.3 Pharmacokinetic Assessment

9.3.1 Pharmacokinetic Analysis

Pharmacokinetic parameter estimates will be determined using non-compartmental procedures in validated software program (Phoenix WinNonlin Version 6.4 or later).

Plasma concentrations of lasmiditan (LY573144) and its metabolites (M7, M8, (S,R)-M18 and (S,S)-M18) will be used to determine the following PK parameters, when possible:

Parameter	Units	Definition
C_{\max}	ng/mL	maximum observed drug concentration
t_{\max}	h	time of maximum observed drug concentration
$AUC(0-\infty)$	ng.h/mL	area under the concentration versus time curve from time zero to infinity
$AUC(0-t_{\text{last}})$	ng.h/mL	area under the concentration versus time curve from time zero to time t , where t is the last time point with a measurable concentration
% $AUC(t_{\text{last}}-\infty)$	%	percentage of $AUC(0-\infty)$ extrapolated
$t_{1/2}$	h	half-life associated with the terminal rate constant (λ_z) in non-compartmental analysis
CL/F	L/h	apparent total body clearance of drug calculated after extra-vascular administration (LY573144 only)
V_z/F	L	apparent volume of distribution during the terminal phase after extra-vascular administration (LY573144 only)
V_{ss}/F	L	apparent volume of distribution at steady state after extra-vascular administration (LY573144 only)
MR		metabolic ratio ^a

^a no molar correction will be applied since the metabolites are very similar in molecular weight and within 5% of the molecular weight for lasmiditan.

Additional PK parameters may be calculated, as appropriate. The software and version used for the final analyses will be specified in the clinical study report. Any exceptions or special handling of data will be clearly documented within the final study report.

Formatting of tables, figures and abbreviations will follow the Eli Lilly Global PK/PD/TS Tool: NON-COMPARTMENTAL PHARMACOKINETIC STYLE GUIDE. The version of the tool effective at the time of PK analysis will be followed.

General PK Parameter Rules

- Actual sampling times will be used in the final analyses of individual PK parameters, except for non-bolus pre-dose sampling times which will be set to zero.
- C_{\max} and t_{\max} will be reported from observed values. If C_{\max} occurs at more than one time point, t_{\max} will be assigned to the first occurrence of C_{\max} .
- AUC parameters will be calculated using a combination of the linear and logarithmic trapezoidal methods (linear-log trapezoidal rule). The linear trapezoidal method will be applied up to t_{\max} and then the logarithmic trapezoidal method will be used after t_{\max} . The minimum requirement for the calculation of AUC will be the inclusion of at least three consecutive plasma concentrations above the lower limit of quantification (LLOQ), with at least one of these concentrations following C_{\max} .
- AUC($0-\infty$) values where the percentage of the total area extrapolated is more than 20% will be flagged. Any AUC($0-\infty$) value excluded from summary statistics will be noted in the footnote of the summary table.
- Half-life ($t_{1/2}$) will be calculated, when appropriate, based on the apparent terminal log-linear portion of the concentration-time curve. The start of the terminal elimination

phase for each subject will be defined by visual inspection and generally will be the first point at which there is no systematic deviation from the log-linear decline in plasma concentrations. Half-life will only be calculated when a reliable estimate for this parameter can be obtained comprising of at least 3 data points. If $t_{1/2}$ is estimated over a time window of less than 2 half-lives, the values will be flagged in the data listings. Any $t_{1/2}$ value excluded from summary statistics will be documented in the footnote of the summary table.

- A uniform weighting scheme will be used in the regression analysis of the terminal log-linear portion of the concentration-time curve.
- The parameters based on last predicted quantifiable drug concentration (C_{last}) will be reported.

Individual PK Parameter Rules

- Only quantifiable concentrations will be used to calculate PK parameters with the exception of special handling of certain concentrations reported below the lower limit of quantitation (BQL). Plasma concentrations reported as BQL will be set to a value of zero when all of the following conditions are met:
 - The compound is non-endogenous.
 - The samples are from the initial dose period for a subject or from a subsequent dose period following a suitable wash-out period.
 - The time points occur before the first quantifiable concentration.
- All other BQL concentrations that do not meet the above criteria will be set to missing.
- Also, where two or more consecutive concentrations are BQL towards the end of a profile, the profile will be deemed to have terminated and therefore any further quantifiable concentrations will be set to missing for the calculation of the PK parameters unless it is considered to be a true characteristic of the profile of the drug.

Individual Concentration vs. Time Profiles

- Individual concentrations will be plotted utilizing actual sampling times.
- The terminal point selections will be indicated on a semi-logarithmic plot.

Average Concentration vs. Time Profiles

- The average concentration profiles will be graphed using scheduled (nominal) sampling times.
- The average concentration profiles will be graphed using arithmetic average concentrations.
- The pre-dose average concentration for single-dose data from non-endogenous compounds will be set to zero.
- Concentrations at a sampling time exceeding the sampling time window specified in the protocol, or $\pm 10\%$, will be excluded from the average concentration profiles.
- Concentrations excluded from the mean calculation will be documented in the final study report.

- A concentration average will be plotted for a given sampling time only if 2/3 of the individual data at the time point have quantifiable measurements that are within the sampling time window specified in the protocol or $\pm 10\%$. An average concentration estimated with less than 2/3 but more than 3 data points may be displayed on the mean concentration plot if determined to be appropriate and will be documented within the final study report.

Treatment of Outliers during Pharmacokinetic Analysis

Application of this procedure to all pharmacokinetic analyses is not a requirement. Rather, this procedure provides justification for exclusion of data when scientifically appropriate. This procedure describes the methodology for identifying an individual value as an outlier for potential exclusion, but does not require that the value be excluded from analysis. The following methodology will not be used to exclude complete profiles from analysis.

Data within an Individual Profile

A value within an individual profile may be excluded from analysis if any of the following criteria are met:

- For pharmacokinetic profiles during single dosing of non-endogenous compounds, the concentration in a pre-dose sample is quantifiable.
- For any questionable datum that does not satisfy the above criteria, the profile will be evaluated and results reported with and without the suspected datum.

Data between Individual Profiles

1. If $n < 6$, then the dataset is too small to conduct a reliable range test. Data will be analyzed with and without the atypical value, and both sets of results will be reported.
2. If $n \geq 6$, then an objective outlier test will be used to compare the atypical value to other values included in that calculation:
 - a. Transform all values in the calculation to the logarithmic domain.
 - b. Find the most extreme value from the arithmetic mean of the log transformed values and exclude that value from the dataset.
 - c. Calculate the lower and upper bounds of the range defined by the arithmetic mean $\pm 3 \times \text{SD}$ of the remaining log-transformed values.
 - d. If the extreme value is within the range of arithmetic mean $\pm 3 \times \text{SD}$, then it is not an outlier and will be retained in the dataset.
 - e. If the extreme value is outside the range of arithmetic mean $\pm 3 \times \text{SD}$, then it is an outlier and will be excluded from analysis.

If the remaining dataset contains another atypical datum suspected to be an outlier and $n \geq 6$ following the exclusion, then repeat step 2 above. This evaluation may be repeated as many times as necessary, excluding only one suspected outlier in each iteration, until all data remaining in the dataset fall within the range of arithmetic mean $\pm 3 \times \text{SD}$ of the log-transformed values.

Reporting of Excluded Values

Individual values excluded as outliers will be documented in the final report. Approval of the final report will connote approval of the exclusion.

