9.3.2 Pharmacokinetic Statistical Methodology

All PK parameters will be summarised by population, as well as population and sex for each treatment, and listed. Plots of mean (+/- SD) plasma concentrations by population, as well as population and sex for each treatment over time will be presented.

Pharmacokinetic parameters for lasmiditan will be evaluated to determine dose proportionality for Japanese (Cohorts 1 and 2 over the 50 to 400 mg dose range, excluding any data from Period 3 in Cohort 2) and Caucasian subjects (Cohort 3, over the 50 to 200 mg dose range). Log-transformed C_{max} and AUC from time 0 extrapolated to infinity [AUC(0- ∞)] will be evaluated using a power model (where the log of the dose will be an explanatory variable and subject will be a random effect) to estimate ratios of dose-normalized geometric means and the corresponding 90% confidence intervals (CIs). The estimated ratio between the highest and lowest doses for each population (Japanese, Caucasian) will be used to assess dose proportionality. The intersubject coefficient of variation (CV) will be derived, and the intrasubject CV will also be derived, as appropriate.

Example SAS code:

```
proc mixed data=pk01;
  by popul param;
  title1 j=c "Estimate of slope";
  class usubjid;
  model log_pk = log_dose / solution residual cl alpha=0.1;
  random usubjid;
  ods output solutionf=doseprop;
run;
```

Additional analysis will be performed if warranted upon review of the data.

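### At the planned six values per cell, the SAP's between-profile outlier test can class a valid PK value as an outlier in up to about 31% of clean cells, and step 2e then removes it

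*SAP*

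**What the plan says.** The between-profile rule in SAP section 9.3.1 depends on the number of values.

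- **Fewer than six:** "then the dataset is too small to conduct a reliable range test". The handling is then: "Data will be analyzed with and without the atypical value, and both sets of results will be reported".
- **Six or more:** an atypical value is put through a test. Step 2b reads: "Find the most extreme value from the arithmetic mean of the log transformed values and exclude that value from the dataset". Step 2c forms the mean ± 3 SD of the remaining log values. Under step 2e, if the value lies outside that range, "then it is an outlier and will be excluded from analysis". The test may be repeated while at least six values remain.

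The preamble to the same procedure is permissive. It says "Application of this procedure to all pharmacokinetic analyses is not a requirement", and that the method identifies a value for possible exclusion "but does not require that the value be excluded from analysis". Excluded values are documented in the final report.

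SAP section 9.3.2 sets where the rule would apply: "All PK parameters will be summarised by population, as well as population and sex for each treatment". It also plans a variability output: "The intersubject coefficient of variation (CV) will be derived".

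**The concern.** Three things looked wrong.

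1. **The limits are too tight for six values.** Leaving out the most extreme value before computing the SD, and then comparing it with a fixed multiple of that SD, makes no allowance for having picked the maximum or for estimating the SD from five values. Five is a number the SAP itself treats as too few for a range test.
2. **The text conflicts.** The preamble says exclusion is not required and step 2e says it happens. The same flagged value could be kept or dropped with equal support from the SAP.
3. **Tables could disagree.** A population-by-sex cell holds about three values and falls under with-and-without reporting. The matching population cell holds six and falls under exclusion. If the rule is applied table by table, one value is treated in two ways.

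At stake are the PK summaries and the power model, which serve the secondary objective. A valid high or low Cmax or AUC could be removed on a test described as objective, and the reported geometric and intersubject CVs would then be too small.

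**Working it through.** **Cell sizes.** Inputs: about 2 completers per sequence (SAP section 7) and the sequence tables (SAP section 5). The plan's totals are reproduced: 7 sequences × 2 = 14 Japanese and 4 × 2 = 8 Caucasian subjects.

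| Population | Treatment | Sequences giving it | Values |
|---|---|---|---|
| Japanese | 50, 100, 200 mg (each) | 2 in Cohort 1 + 1 in Cohort 2 | 3 × 2 = 6 |
| Japanese | 400 mg | 3 in Cohort 2 | 6 |
| Japanese | 2 × 200 mg | 3 in Cohort 2 | 6 |
| Caucasian | 50, 100, 200 mg (each) | 3 in Cohort 3 | 6 |

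All 8 active cells have n = 6, the smallest n at which the SAP moves from with-and-without reporting to exclusion. The power model has 4 × 6 = 24 Japanese values and 3 × 6 = 18 Caucasian values; Japanese 2 × 200 mg is not in it.

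**Flag rate on clean log-normal data, test run on every cell.** Closed form: n × 2P(t with n−2 df > 3/√(1 + 1/(n−1))).

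At n = 6: 3/√1.2 = 2.739; 2P(t₄ > 2.739) = 0.0520; 6 × 0.0520 = 31.2%. Simulating steps 2a to 2e gives the same result to within simulation error:

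| n | 6 | 7 | 8 | 14 | 20 | 50 | 100 |
|---|---|---|---|---|---|---|---|
| Flag rate | 31% | 27% | 25% | 19% | 18% | 22% | 32% |

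Over 8 cells, 8 × 0.312 = 2.5 valid values would be flagged per parameter. At n = 6 the rate would be 1.6% if the mean and SD were known, and 3.7% if only the SD were known.

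**What 3 SD of the other five means.** Give the other five mean 0 and SD 1 (sum of squares 4) and put the sixth at 3. The overall mean is 0.5, so the deviation is 2.5. The total sum of squares is 4 + (5/6) × 9 = 11.5. The value lies 2.5/√(11.5/5) = 1.65 SDs of the full six from their mean.

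**Flag rate at n = 6 if only suspect values are tested.** The SAP defines neither a trigger nor a CV, so both are assumptions. Distance is measured from the geometric mean of the rest.

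| Trigger | CV 20% | CV 30% | CV 50% |
|---|---|---|---|
| At least 1.5-fold away | 15% | 26% | 30% |
| At least 2-fold away | 0.7% | 9% | 25% |

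With every cell tested at CV 30%, the median flagged valid value is only 1.8-fold from the rest.

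**Effect on variability at n = 6.** With every cell tested, the log variance is 22% too small. At a true CV of 30% the mean geometric CV is 24% instead of 29%, and in cells where a value was removed 15% instead of 29%. At CV 30%, a 1.5-fold trigger cuts the log variance by 21% and a 2-fold trigger by 12%.

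**Effect on the power model.** The planned sequences were simulated with 3,000 REML random-intercept fits per population for each of four assumed (between, within) log-SD pairs: (0.2, 0.15), (0.3, 0.2), (0.4, 0.2) and (0.3, 0.3). With the rule run on every dose cell, between-subject variance falls 17–25%, the 90% CI half-width for the slope is essentially unchanged, and coverage falls from 89–90% to 85–87%.

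**The case against.** The strongest reply is that 31% and the effects with every cell tested describe a use the SAP does not prescribe. The test is for an atypical value and the preamble leaves its use to judgement. With a 2-fold trigger at n = 6, the mean geometric CV is 27% instead of 29% at a true 30%, and 18.9% instead of 19.1% at a true 20%. In the power model with that trigger, 90% CI coverage stays within about 1 point of the no-exclusion result (800 fits per setting, two of the four variance pairs). This stands: 31% is an upper bound. But the rate is small only with a low CV and a strict trigger, and the SAP sets no trigger. Even with the 2-fold trigger, the mean geometric CV at a true 50% is 42% instead of 48%, and between-subject variance in the model falls about 9–16%.

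Second, n = 6 is not the whole cause: the rate is as high at n = 100. That is correct. A fixed 3-SD limit ignores selection of the maximum at any n, which argues for a remedy at every n.

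Third, the model effect assumes cell-level flags carry into the model. If the comparison set is instead all values in the model, the trigger rate is 0–4% on raw values and 12–17% on dose-normalised values. The table conflict likewise assumes the rule is applied table by table. The SAP settles neither reading, so both points stand as conditions.

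Finally, exclusions are documented, listings keep the data, PK is a secondary objective, and one changed word in step 2e would remove the textual conflict. All true. The one word would still leave a test that flags valid values this often as the stated justification for removing them.

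**Conclusion.** The concern holds, and the rule should be fixed. At n = 6, the planned size of every active cell, the test classes a valid value as an outlier in up to 31% of clean cells, and step 2e prescribes exclusion against the SAP's own preamble. The damage is to reported variability: log variance is up to 22% too small, and 12–21% too small at an assumed CV of 30% with 2-fold or 1.5-fold triggers. Cell geometric means are not biased on clean data, and the data remain visible in listings.

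This rests on log-normal data, an SD with divisor one less than the number of values, and two completers per sequence. Actual cells may differ: seven or eight values still give 25–27%, while one missing value makes n = 5 and brings with-and-without reporting. In a cell of six at most one value can go, because five remain and the iteration stops.

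**What to change.** In SAP section 9.3.1:

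- Reconcile step 2e with the preamble. Replace mandatory exclusion with the SAP's existing handling for fewer than six values, applied at every n: all values stay in the primary summaries and the power model, and results are reported with and without any flagged value.
- Leave a value out of the primary analysis only for a documented cause: an assay, dosing or sampling error, or the vomiting rule in SAP section 8.
- State that the comparison set in step 2 is the population-by-treatment cell.
- Optionally, keep a numerical flag that depends on n and only triggers the with-and-without result. For a 5% false-flag rate the multiplier is t(1 − 0.05/(2n), n−2 df) × √(1 + 1/(n−1)), about 5.3 at n = 6.

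The cost is SAP wording and one duplicate summary per flagged value. Reported CVs become somewhat larger. A true outlier with no documented cause stays in the primary summary, with the result without it alongside.

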9.3.2 Pharmacokinetic Statistical Methodology

All PK parameters will be summarised by population, as well as population and sex for each treatment, and listed. Plots of mean (+/- SD) plasma concentrations by population, as well as population and sex for each treatment over time will be presented.

Pharmacokinetic parameters for lasmiditan will be evaluated to determine dose proportionality for Japanese (Cohorts 1 and 2 over the 50 to 400 mg dose range, excluding any data from Period 3 in Cohort 2) and Caucasian subjects (Cohort 3, over the 50 to 200 mg dose range). Log-transformed C_{max} and AUC from time 0 extrapolated to infinity [AUC(0- ∞)] will be evaluated using a power model (where the log of the dose will be an explanatory variable and subject will be a random effect) to estimate ratios of dose-normalized geometric means and the corresponding 90% confidence intervals (CIs). The estimated ratio between the highest and lowest doses for each population (Japanese, Caucasian) will be used to assess dose proportionality. The intersubject coefficient of variation (CV) will be derived, and the intrasubject CV will also be derived, as appropriate.

Example SAS code:

```
proc mixed data=pk01;
  by popul param;
  title1 j=c "Estimate of slope";
  class usubjid;
  model log_pk = log_dose / solution residual cl alpha=0.1;
  random usubjid;
  ods output solutionf=doseprop;
run;
```

Additional analysis will be performed if warranted upon review of the data.

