## 5.4. Scientific Rationale for Study Design

A subject- and investigator-blinded, randomized, and placebo-controlled design has been chosen to minimize bias in the primary objective of this study, and a crossover design has been chosen to minimize the number of subjects required for the study. The study design that has been chosen is considered to be the most feasible to execute operationally. As this will be the first time that the commercial formulation of lasmiditan will be administered to humans, Caucasian

subjects have been included to allow comparisons between Japanese and Caucasian subjects to be made.

Single and repeated doses (2 single doses administered 2 hours apart) of 50, 100, and 200 mg lasmiditan are considered the planned clinical doses. Additionally, a supratherapeutic dose of 400 mg lasmiditan has been included for the assessment of QT interval. As patients currently receiving approved therapies for migraine may administer an additional dose 2 hours following their initial dose if symptoms do not alleviate, this study will also evaluate the safety, tolerability, and PK of 2 doses of 200 mg lasmiditan administered 2 hours apart.

Pharmacokinetic sampling time points have been selected to generate PK profiles sufficient to fulfill the study objectives.

Conducting the study in healthy subjects mitigates the potential confounding effects of the disease state and concomitant medications in patients. Healthy subjects are frequently used in the assessment of bioavailability of both small and large molecules. Conducting this study in Japanese subjects will support their inclusion in future studies with lasmiditan, and inclusion of Caucasian subjects enables the direct comparison between Japanese and Caucasian subjects.

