### 10.3. Statistical Analyses

Statistical analysis of this study will be the responsibility of Eli Lilly and Company or its designee.

Pharmacokinetic analyses will be conducted on data from all subjects who receive at least one dose of the investigational product and have evaluable PK. Safety analyses will be conducted for all enrolled subjects, whether or not they completed all protocol requirements.

Additional exploratory analyses of the data will be conducted as deemed appropriate. Study results may be pooled with the results of other studies for population PK analysis.

Where applicable, safety and PK data will be presented separately for Japanese and Caucasian subjects.

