4.3 Exploratory Objectives

- To evaluate the PK of metabolites M7, M8, (S,R)-M18, and (S,S)-M18 in healthy Japanese and Caucasian subjects.
- To explore the safety, tolerability, and PK of lasmiditan in female subjects compared to male subjects.

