9. STATISTICAL METHODOLOGY

9.1 General

Data listings will be provided for all data that are databased. Summary statistics and statistical analysis will only be presented for data where detailed in this SAP. For continuous data, summary statistics will include the arithmetic mean, arithmetic standard deviation (SD), median, min, max and N; for log-normal data (e.g. the PK parameters: area under the concentration versus time curve [AUCs] and maximum observed drug concentration [C_{max}]) the geometric mean and geometric coefficient of variation (CV%) will also be presented. For categorical data, frequency count and percentages will be presented. Data listings will be provided for all subjects up to the point of withdrawal, with any subjects excluded from the relevant population highlighted. Summary statistics and statistical analyses will generally only be performed for subjects included in the relevant analysis population. For the calculation of summary statistics and statistical analysis, unrounded data will be used.

Mean change from baseline is the mean of all individual subjects' change from baseline values. Each individual change from baseline will be calculated by subtracting the individual subject's baseline value from the value at the time point. The individual subject's change from baseline values will be used to calculate the mean change from baseline using a SAS procedure such as Proc Univariate.

Data analysis will be performed using SAS[®] Version 9.4 or greater.

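### The SAP gives no female/male or Japanese/Caucasian exposure ratio with a confidence interval, although one sex term and one reported contrast would supply both at almost no cost

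*SAP*

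**What the plan says.** The model in SAP Section 9.3.2 regresses log Cmax and log AUC(0-∞) on log dose, "where the log of the dose will be an explanatory variable and subject will be a random effect". The example code agrees: the model line is "model log_pk = log_dose / solution residual cl alpha=0.1" and the fits are split with "by popul param". The 90% intervals serve the highest-versus-lowest dose comparison within each population. The Japanese fit uses single doses of 50 to 400 mg without Cohort 2 Period 3; the Caucasian fit uses 50 to 200 mg.

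Elsewhere in the PK analysis, population and sex only group the output: "All PK parameters will be summarised by population, as well as population and sex for each treatment, and listed". SAP Section 9.1 adds that for log-normal parameters "the geometric mean and geometric coefficient of variation (CV%) will also be presented". Protocol Section 10.3 takes the same line: "Where applicable, safety and PK data will be presented separately for Japanese and Caucasian subjects".

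On purpose, Protocol Section 5.4 says that "inclusion of Caucasian subjects enables the direct comparison between Japanese and Caucasian subjects", and SAP Section 4.3 lists as an exploratory objective: "To explore the safety, tolerability, and PK of lasmiditan in female subjects compared to male subjects". Randomization is stratified by sex (Protocol Section 7.2).

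**The concern.** Two comparisons that the documents give as purposes have no planned estimate with a measure of uncertainty. For sex, the model contains no sex term, so the planned output is a set of geometric means and CVs by dose, population and sex. From those a reader can form a ratio, or build an interval by hand, only within one small cell at a time. For population, each planned fit already combines doses, but the SAP never asks for the difference between the two fitted lines.

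The study is not powered for tests (SAP Section 7), so an estimate with its interval is the useful answer to both questions. Protocol Section 3.2 cites a female excess of about 20% to 30% in Cmax and 30% in AUC from a previous study, and per-dose tables with 3 per sex say little about a difference of that size. A model chosen after the data are seen would not be prespecified.

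**Working it through.** **Plan's own figures.** Two completers per sequence: Japanese 2 × (3 + 4) = 14, Caucasian 2 × 4 = 8. Both match SAP Section 7.

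**Records available.** From the sequence tables, leaving out placebo and Cohort 2 Period 3, and assuming one male and one female completer per sequence:
- Japanese: 6 records at each of 50, 100, 200 and 400 mg, so 24 records from 14 subjects (10 subjects with two records, 4 with one).
- Caucasian: 6 records at each of 50, 100 and 200 mg, so 18 records from 8 subjects (6 with two, 2 with three).
- Total: 42 records from 22 subjects; 3 per sex at each dose within a population.

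**Variances (assumed).** Log-scale variance is ln(1 + CV²). For between/within CVs of 20/15, 30/20 and 40/25%, the pairs (σb², σw²) are (0.0392, 0.0223), (0.0862, 0.0392) and (0.1484, 0.0606).

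**One dose, one population, 3 vs 3.** The multiplier is exp{t(0.95; 4 df) × √[(σb² + σw²) × 2/3]}. At 30/20: exp(2.132 × √0.0836) = exp(0.616) = 1.85.

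**Sex from a model over all doses.** A subject with k records carries weight w(k) = k/(σw² + kσb²). With the sexes balanced within each sequence, the sex contrast is orthogonal to dose, and its variance is 4/Σw. At 30/20, w(1) = 7.97, w(2) = 9.45, w(3) = 10.08.
- Japanese: Σw = 10 × 9.45 + 4 × 7.97 = 126.4; variance 0.0316; SE 0.178; 18 df; exp(1.734 × 0.178) = 1.36.
- Caucasian: Σw = 6 × 9.45 + 2 × 10.08 = 76.9; variance 0.0520; SE 0.228; 18 df; exp(1.734 × 0.228) = 1.49.
- Pooled, common sex effect: Σw = 203.3; variance 0.0197; SE 0.140; 19 df; exp(1.729 × 0.140) = 1.27.
- Sex-by-population interaction: variance 0.0316 + 0.0520 = 0.0837 before rounding; SE 0.289; exp(1.734 × 0.289) = 1.65.

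**Population at 100 mg.** The two fits use different people, so their variances add. At 30/20, generalised least squares gives a fitted log mean at 100 mg with variance 0.0085 (Japanese) and 0.0130 (Caucasian). The sum is 0.0216 and the SE 0.147. With 20 df this is exp(1.725 × 0.147) = 1.29. A joint model with a population-by-log-dose term gives the same value to two decimals.

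| 90% CI multiplier (×/÷) | 20/15 | 30/20 | 40/25 |
|---|---|---|---|
| Sex, one dose, one population (3 vs 3) | 1.54 | 1.85 | 2.22 |
| Sex, Japanese, all single doses | 1.24 | 1.36 | 1.49 |
| Sex, Caucasian, all single doses | 1.31 | 1.49 | 1.67 |
| Sex, one dose, pooled over populations (6 vs 6) | 1.30 | 1.45 | 1.62 |
| Sex, pooled, all single doses | 1.18 | 1.27 | 1.37 |
| Population at 100 mg, two planned fits | 1.19 | 1.29 | 1.39 |
| Population at 100 mg, joint model | 1.19 | 1.29 | 1.39 |

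**What this means for a 30% difference.** At 30/20, an observed ratio of 1.30 would have an interval of 0.70 to 2.41 from one dose in one population (1.30 ÷ and × 1.85). It would be 0.96 to 1.77 in Japanese subjects over all doses (1.36), and about 1.02 to 1.66 pooled (1.274).

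**Effect of the 400 mg records.** Restricting to 50–200 mg leaves 36 records from 20 subjects. At 30/20 the Japanese sex multiplier rises from 1.36 to 1.41 and the pooled one from 1.27 to 1.29.

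**The case against.** The plan largely does what the protocol says. The secondary objective is to evaluate PK in each population, and the sex objective is only to explore. Protocol Section 10.3.2.2 treats separate presentation of the sexes as the way to explore a sex effect, and it allows the populations to be pooled. Both documents leave room for additional analysis, and all PK parameters are listed by subject. A reader might infer that a promised analysis is missing. The documents do not support that: no listed objective promises a population contrast, and descriptive tables can count as exploration.

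A reader might also infer that populations can be compared only one dose at a time, and that a joint model would sharpen the comparison. That is wrong as well. The planned fits already combine doses, and the difference between them at 100 mg is as precise as the joint model's. Only the reporting is missing: log dose centred at the reference dose, or the intercept–slope covariance printed.

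The new output would also settle little. At 30/20 the pooled sex interval is about as wide as the 20–30% difference of interest, and the check of a common sex effect (×/÷1.65) is weak.

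What remains is that the permissions are optional or triggered by the data, none names a ratio or an interval, and no planned PK model contains sex.

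**Conclusion.** The point holds as a low-cost exploratory improvement. No planned result is invalid. For sex the gain is real: at 30/20 the multiplier falls from 1.85 to 1.36 in Japanese subjects and to 1.27 pooled. Part of the pooled gain comes from combining populations (1.85 to 1.45 at one dose) and the rest from combining doses (1.45 to 1.27). For population the gain is a stated contrast with an interval of about ×/÷1.19 to 1.39 over the assumed CVs, and no added precision.

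The sizes rest on assumed CVs and on exactly one male and one female completer per sequence. The documents promise only about two per sequence and roughly equal sexes per cohort. The pooled sex figure also needs a common sex effect.

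**What to change.** Keep the by-population power models for dose proportionality. Add to SAP Section 9.3.2 one prespecified exploratory mixed model for log Cmax and log AUC(0-∞), on the single-dose data already used there (50–400 mg, Cohort 2 Period 3 excluded). Its terms are log dose, population, sex, population-by-log-dose and random subject. Report, each with a 90% interval:
- the female/male geometric mean ratio overall, and within each population after adding a sex-by-population term;
- the Japanese/Caucasian ratio at a named dose that both populations receive, for example 100 mg, from this model or equivalently from the two planned fits.

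A 50–200 mg run may serve as a sensitivity check.

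Label all of it as exploratory estimation and state the caveats. Population is not randomised (Protocol Section 7.2), and diet may differ (Section 6.3.1). Dose and period are not balanced alike across cohorts: in Cohort 3 each dose occurs in one period only, while some Japanese subjects receive 100 or 200 mg in Period 1. The ratios are not adjusted for body weight. If unblinded data have already been reviewed, call the model post hoc.

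The cost is one paragraph of SAP text and a few extra PROC MIXED runs, with no new subjects or samples.
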